4.7 Subject Withdrawal

It is recognized that the subject's participation in this trial is entirely voluntary, and that she/he may refuse to participate and may withdraw from participation at any time without jeopardy to any future medical care. It is also recognized that the investigator, at his/her discretion, may withdraw a subject from this study based upon his/her professional judgment. If the subject is withdrawn for any reason at any time a final evaluation form will be completed and the Sponsor will be notified.

Other Conditions for Withdrawal:

Any subject who develops a severe concurrent medical illness during the trial should be withdrawn. This type of illness is defined as any illness that would hinder the subject's ability to return for scheduled follow-up appointments. Such a withdrawal will not be counted for the purposes of determining success or failure.

5 STATISTICAL ANALYSIS PLAN

Statistical analyses will be performed as deemed appropriate to evaluate different healing outcomes across the various patient populations.

Primary outcome analysis to assess the final fusion status of all enrolled patients will be performed prospectively by the former principal investigator, Dr. [name]. Following his departure from The Ohio State University, the investigator(s) will review the 12 month CT scans to evaluate each subject for radiographic success, partial success, or failure.

In case early findings reveal a statistical difference in fusion grades comparing the sides of autograft and ViviGen Cellular Bone matrix, enrollment will cease as investigators are unlikely to maintain clinical equipoise. Similarly, if the analysis suggests it is unlikely the study will achieve statistical significance, the investigators may choose to close the trial early for futility. Currently enrolled subjects will be followed throughout the remainder of the study, up to 12 months post-surgery.

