4.2 Surgical Procedure

After receiving antibiotic prophylaxis, the patient is placed under general anesthesia and positioned prone. A midline posterior approach is performed, exposing the posterior lumbar elements including the facet joints. Polyaxial pedicle screws are placed bilaterally, using fluoroscopic guidance, depending on preference of the surgeon.

In cases of neurogenic claudication related to spinal canal stenosis, the central part of the spinal canal is decompressed by laminectomy. In cases of radicular leg pain related to foraminal stenosis, partial facetectomies will be performed as needed to decompress the associated nerve roots.

Titanium rods are then positioned interconnecting the screws on each side. The posterolateral cortical bony surfaces are then fully decorticated and supplemented with milled local autograft bone on one side and an equal volume of Depuy Synthes ViviGen on the other side.

Data will be collected during and immediately after the surgery according to the parameters described by the ViviGen Lumbar study CRFs. This includes: diagnosis, duration of surgery, blood loss, OR time, length of hospital stay, instrumentation used, type of procedure, and surgical level(s). In addition, all intraoperative complications (e.g. excessive blood loss, hematoma, vascular injury, etc.) will be reported and recorded as a complication in the study CRFs.

Intra-operative (after hardware installation is completed) and immediate post-operative x-rays will be obtained. Postoperative care will follow the standard of care for subjects who undergo fusion procedures.

Postoperative care is extremely important. The subjects will be warned that noncompliance with postoperative instructions could lead to breakage of the pedicle screw system requiring revision surgery.

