4.5 Fusion Determination

Fusion will be assessed by an independent radiologist using the subjects' 12 month visit CT images. The extent of fusion will be determined using the Lenke classification. The scale is as follows:

- Grade A - Definitely solid with bilateral trabeculated stout fusion masses present
- Grade B - Possibly solid with a unilateral large fusion mass and a contralateral small fusion mass
- Grade C - Probably not solid with a small fusion mass bilaterally
- Grade D - Definitely not solid with bone graft resorption or obvious pseudoarthrosis bilaterally

Radiographic success: radiographic success is defined as grade A.

Partial radiographic success: partial radiographic success is defined as grade B. Images graded as "B" will be subcategorized by the location of the unilateral large fusion mass (autograft side, B-a vs. ViviGen side, B-v).

Radiographic Failure: radiographic failure is defined as grades C or D.

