4.6 Success Criteria

4.6.1 Primary Objective

A subject outcome will be considered a success if fusion is graded as a Grade A. A subject outcome will be considered a partial success if fusion is graded as a Grade B. Images graded as "B" will be subcategorized by the location of the unilateral large fusion mass (autograft side, B-a vs. ViviGen side, B-v).

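### Sections 4.5 and 5 give the primary 12-month CT classification to different readers, and the plan does not say whose reading counts

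*Combined protocol and SAP*

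**What the plan says.** - **Section 4.5 (Fusion Determination):** "Fusion will be assessed by an independent radiologist", using the 12-month CT and the Lenke scale. A is success, B is partial success, and C or D is failure. Grade B scans are also "subcategorized by the location of the unilateral large fusion mass (autograft side, B-a vs. ViviGen side, B-v".
- **Section 4.6.1 (Primary Objective):** "A subject outcome will be considered a success if fusion is graded as a Grade A". This makes the CT grade the primary outcome. The section names no reader.
- **Section 5 (Statistical Analysis Plan):** the primary outcome analysis of final fusion status "will be performed prospectively by the former principal investigator". After that person's departure, "the investigator(s) will review the 12 month CT scans to evaluate each subject for radiographic success, partial success, or failure". The radiologist is not mentioned. The section adds that if early findings show a statistical difference between the graft sides, "enrollment will cease as investigators are unlikely to maintain clinical equipoise".
- **Section 4.2 (Surgical Procedure):** each subject receives "milled local autograft bone on one side and an equal volume of Depuy Synthes ViviGen on the other side". Left or right is not fixed. Operative data are collected "according to the parameters described by the ViviGen Lumbar study CRFs"; those forms are not among the documents.

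**The concern.** The primary endpoint is a reader's judgement, and the plan gives that judgement to two different parties. The line between A and B turns on whether the second fusion mass is stout or small, and only A counts as success. If both reads exist and differ, the plan does not say which one enters the analysis, so the choice could be made with both results in view. If only the investigators read the scans, the independence promised in section 4.5 is lost.

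There is a secondary gap. No supplied section masks any reader to graft side, although Grade B is split by graft side and a side difference stops enrollment. Being independent is not the same as being masked.

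**Working it through.** **Step 1. Set the sections side by side.**

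| | Section 4.5 | Section 5 |
|---|---|---|
| Images | 12-month CT | 12-month CT |
| Categories | success, partial success, failure | success, partial success, failure |
| Reader | independent radiologist | former principal investigator (analysis), then the investigator(s) |
| Read of record | not stated | not stated |
| Rule for disagreement | none | none |

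The images and categories match, and the readers do not. No other supplied section settles the matter.

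**Step 2. Is there a figure to reproduce?** No. The documents give no sample size, test, alpha, grade distribution or reader agreement. Steps 3 and 4 are exact calculations on assumed inputs and show scale only. N is the number of subjects with a graded 12-month CT.

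**Step 3. Two reads, no read of record, neither reader biased.** Let d be the assumed proportion of subjects on whom the reads disagree about A versus not-A, equally often in each direction. The number of disagreements is D ~ Binomial(N, d), of which K ~ Binomial(D, 0.5) go one way. The gap between the two success rates is |2K − D| / N. Its mean, in percentage points, is:

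| d | N=30 | N=50 | N=100 |
|---|---|---|---|
| 10% | 4.4 | 3.5 | 2.5 |
| 20% | 6.4 | 5.0 | 3.6 |
| 30% | 7.9 | 6.1 | 4.4 |

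**Step 4. Reader not masked to side (secondary).** Assume no true side difference, Grade B in a proportion pB = 40% of subjects split evenly between B-a and B-v, and one look with an exact McNemar test at two-sided 0.05. Suppose a fraction f of B-a scans is read up to A because the ViviGen side is graded leniently. Then P(B-v) = pB/2 = 0.20 and P(B-a) = (pB/2)(1 − f). With f = 30%, P(B-a) = 0.20 × 0.70 = 0.14. The number of discordant subjects is Binomial(N, P(B-v) + P(B-a)). The false-positive rate is:

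| f | N=30 | N=100 |
|---|---|---|
| 0 | 2.4% | 3.5% |
| 10% | 2.6% | 4.3% |
| 20% | 3.2% | 7.4% |
| 30% | 4.4% | 13.3% |

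If the same leniency falls on both sides, P(B-v) = P(B-a) = (pB/2)(1 − f). The rate then stays at or below about 4.0% over N = 10 to 200, for pB of 20%, 40% or 60% and f from 0 to 30%.

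**The case against.** **Section 5 may be only a personnel update.** It hands the analysis from a departing investigator to the remaining ones, and it does not say that the radiologist is dropped. Investigators might look at the scans alongside the radiologist's grade. That reading fits the sentence about the former principal investigator. It does not fit the next one, in which the investigators work from the scans themselves and place each subject in a category. What stands is that the documents do not show which reader the sponsor intended.

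**Missing side masking is an omission in a single-arm post-market study, not a contradiction.** This stands. Grade A needs stout masses on both sides, so knowing the graft side affects primary success only through the A/B call. The direct exposure is the B-a/B-v label and the side comparison. Step 4 also models one route, one direction, one look and one test, none of which the plan specifies.

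**Stronger readings that the documents do not support.** A reader might infer that the side comparison is already seriously biased. At N=30 with 40% Grade B, even 30% up-reading leaves the rate at 4.4%, and N is not given. A reader might also infer that withholding the operative notes would guarantee masking. It would not: one side carries milled local autograft and the other a cellular matrix with cortico-cancellous chips and demineralized bone (section 2.2.1), and nothing says that the two look alike on CT.

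**Conclusion.** The concern holds as a contradiction about who determines the primary endpoint, and it must be fixed. That conclusion rests on the text alone and needs no assumed number. It covers the supplied text only; one opening part of the document was removed before review, and the CRFs are not included.

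The possible size is hypothetical. Unbiased reads that disagree on 20% of subjects give success rates 6.4 points apart on average at N=30 and 3.6 at N=100.

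The masking gap is secondary. Under the assumptions of step 4 with 30% up-reading, the false-positive rate rises from 2.4% to 4.4% at N=30 and from 3.5% to 13.3% at N=100, so the effect is small in a small study and larger in a bigger one. The documents do not show that any read has been biased.

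**What to change.** **Main change.** Reconcile sections 4.5 and 5. State that the independent radiologist's Lenke grade is the read of record for every subject's 12-month CT, for the primary outcome and for any interim side comparison, and that any investigator read is supportive only. If the sponsor meant section 5 to replace the radiologist, the protocol should say so and remove the claim of independent assessment from section 4.5.

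**Secondary change.** Have the radiologist grade without operative notes or clinical outcomes and record the large fusion mass in Grade B as left or right. Derive B-a or B-v afterwards from the operative record of graft side, after confirming that the CRF captures it. This reduces knowledge of graft side but does not guarantee masking.

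**Cost.** Wording in two sections and a check of the CRF. No new reader is needed, because the protocol already names the radiologist. The downside is that scans so far read only by an investigator must also go to the radiologist. Section 4.5 already requires that read, but the documents do not say how many scans are affected.
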